9.4.3 ANALYSIS OF THE SECONDARY ENDPOINT(S)

The proportion of participant who complete the 6-month assessment visit will be compared across study arms descriptively. We will use binomial proportion tests to compare the number of website visits by recruitment message type.

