1 PROTOCOL SUMMARY

1.1 SYNOPSIS

[figure not shown]
| | | |
|--|--|---|
| Title: | Engaging men from blue-collar industries in weight loss | |
| Grant Number: | K01DK119457 | |
| Study Description: | | |
| Objectives*: | Primary Objective: | Aim 1: Examine the acceptability of tailored behavioral weight loss program and a standard program in men working in blue-collar occupations. Aim 2: Compare recruitment approaches that vary on trust-based messaging to recruit men with overweight/obesity who work in blue-collar occupations. |
| | Secondary Objectives: | Determine the feasibility of retaining participants to a randomized trial over six months. Determine the reach of recruitment messages. |
| Endpoints*: | Primary Endpoint: | Aim 1: Participant reported satisfaction at 3 months. Aim 2: Proportion of participants who enroll in study by recruitment type |
| | Secondary Endpoints: | Number of visits to recruitment websites by recruitment type. Percentage of participants who complete a weight assessment at the 6-month assessment timepoint. Participant reported satisfaction at 6 months. |
| Study Population: | Men BMI>25 | |
| Phase* or Stage: | Feasibility testing | |
| Description of Sites/Facilities Enrolling Participants: | Single site | |
| Description of Study Intervention/Experimenta l Manipulation: | This protocol is for a randomized pilot study that will test the acceptability of a novel weight loss program and a standard weight loss program in men with overweight or obesity who work in blue-collar occupations. The secondary aim of the study is to test in a randomized comparison the effect of recruitment messages that | |

enhance trust in two ways: researcher trust enhancement (Yes, No)
 endorsement (Yes, No).

Study Duration*: 18 months

Participant Duration: 6 months

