3 OBJECTIVES AND ENDPOINTS

| OBJECTIVES | ENDPOINTS | JUSTIFICATION FOR ENDPOINTS |
|--|--|--|
| Primary | | |
| Aim 1: Examine the acceptability of tailored behavioral weight loss program and a standard program in men working in blue-collar occupations. | Participant reported satisfaction with program acceptability at 3 months. | Participant satisfaction is a proxy for program acceptability. |
| Aim 2: Compare recruitment approaches that vary on trust-based messaging to recruit men with overweight/obesity who work in blue-collar occupations. | Proportion of participants who enroll in study by recruitment message type. | The goal of recruitment is enrollment in the study. Using the proportion of participants who received the postcard as the endpoint provides an assessment of the effectiveness of the message. |
| Secondary | | |
| Determine the feasibility of retaining participants to a randomized trial over six months. | Percentage of participants who complete a weight assessment at the 6-month assessment timepoint. | High retention to the study will indicate the study procedures are feasible for a fully powered trial. |
| Determine the reach of recruitment messages. | Number of visits to recruitment websites. | The website is the first indication of participant interest in the study. |
| Determine the acceptability of the intervention. | Participant reported satisfaction with program at 6 months. | |
| Tertiary/Exploratory | | |
| Determine percentage of participants who achieve a clinically significant weight reduction (5% of initial weight). | Weight objectively assessed by study staff at baseline, 3 months, and 6 months. | 5% weight loss is an established indicator of clinically significant weight loss. |
| Evaluate participants perceptions of program components. | Semi-structured interviews. | We will conduct semi-structured interviews with participants to gain a deeper understanding of their perceptions of program components and their experiences in the program. |

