4 STUDY DESIGN

4.1 OVERALL DESIGN

This study is a two-armed randomized controlled trial with assessments at baseline, 3 months after randomization, and 6 months after randomization. The objective is to assess the acceptability of the intervention to participants at 3 months and the feasibility of study procedures at 6 months with retention to the study as the outcome. This is a single site, Stage 1 study.

Participants will be randomly assigned to study groups by a biostatistician who is not involved with the study assessments or interventions using a random number generator. Individuals will be randomly assigned to study conditions in cohorts of approximately 30 individuals. Randomization will be concealed from participants until their first treatment session.

Participants will be randomized to receive either the tailored BELT (Better Energy through Lifestyle for Tradesmen) treatment or a standard weight loss program (Diabetes Prevention Program Group Lifestyle Balance; DPP GLB). The groups will be matched on number of weeks of treatment, mode of delivery, and contact time.

During recruitment for this study, we will conduct a randomized comparison of recruitment messages. This comparison will use a factorial design testing the effects of enhancing trust in the researchers (Trust Messaging: Yes, No) and the effects of a participant endorsement (Endorsement: Yes, No). Names and addresses for individuals from a purchased marketing list will be randomly assigned to be sent a postcard with a recruitment message matching their assigned condition. Recruitment reach will be assessed through website visits and number of participants responding to each message.

This is a feasibility study with no formal hypotheses to be tested.

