5.5 STRATEGIES FOR RECRUITMENT AND RETENTION

Participants will be recruited via the postcards mailed to their homes. They will be directed to a study website where a brief description of the study will be presented. Participants recruited through the four recruitment messages will be sent to separate but identical websites. Participants who are interested will be asked to complete an online screening form. Those who appear initially eligible will be contacted to schedule a time to attend a study orientation. This orientation will allow participants the opportunity to gain information about the study and to experience the web conferencing platform (if they have not used it before). The session will describe the study and will use the motivational interviewing approach described by Kiernan and colleagues ^{44, 45, 46} to enhance engagement and retention to the study. Following this, participants will attend an in-person assessment visit where they will sign consent before completing the physical measures and self-report questionnaires. Participants who complete the baseline visit and measures will be randomized to receive either the tailored intervention or the generic intervention following a 1:1 randomization ratio.

Recruitment will be supplemented by recruitment through flyers, notices on a hospital "on-hold" line, and online recruitment messages as needed. These potential participants will be encouraged to contact the study through the study website and will go through the recruitment process described above.

All recruitment materials and plans will be reviewed and approved by the Rush University Institutional Review Board prior to implementation.

To maximize retention, we will collect multiple methods for contacting participants (e.g., email, telephone) at baseline. Participants will tentatively schedule their follow-up assessment during their initial treatment session, a method we have used in prior studies to increase retention rates. During the intervention, participants have not engaged with treatment for at least one anticipated sessions will be contacted directly by intervention staff to encourage reengagement with the program.

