6 STUDY INTERVENTION(S) OR EXPERIMENTAL MANIPULATION(S)

6.1 STUDY INTERVENTION(S) OR EXPERIMENTAL MANIPULATION(S) ADMINISTRATION

6.1.1 STUDY INTERVENTION OR EXPERIMENTAL MANIPULATION DESCRIPTION

Recruitment substudy

During recruitment for the trial, we will test the effects of recruitment messages using mailing postcards with four different recruitment messages to addresses of men believed to work in blue-collar occupations. The intervention exposure is the receipt of the postcards by potential participants. The four recruitment messages:

- Standard recruitment message alone (e.g., “Tradesmen: Boost your energy and feel better through changes to eating and physical activity!”)
- Standard message plus messages to enhance trust (e.g., “Join the BELT study: built for tradesmen with tradesmen” and “Why we are doing this: Our team wants to understand how to help men like you improve their health. We’ve developed a new program with input from men like you for men like you. It’s designed to fit into your life!”),
- Standard message plus an endorsement from a prior participant (“This is a great program...safe, thoughtful, and effective.”)
- A combined trust and endorsement message.

An identical description of the program plus a call to action “Go to [study website] to see if you are eligible!] will be included in all postcards. Participants will be sent to separate but identical websites to allow us to track the reach of the messages via the number of independent website visits. The remaining recruitment process will be identical for all participants, regardless of recruitment message received. From the website, participants can choose to be screened for eligibility and will be randomized into the trial as appropriate.

The BELT Intervention

The BELT intervention will be delivered via 16- group session conducted via web-conferencing (i.e., Zoom) supported by short, educational videos hosted on the study website. Online groups sessions will allow participants to give and receive social support from peers while also minimizing disruption to lifestyle that would be needed for a face-to-face group session. Study staff will help troubleshoot any issues using this system during the intervention. Importantly, all participants will have chance to use the platform during the online orientation session for the study. Group sessions will be 60 minutes per session and will occur weekly for months 1-3, twice in month 4, and once a month in months 5 and 6.

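### Website visits are compared across four message types, although the recruitment substudy is a 2x2 factorial whose main effects would answer its question more precisely

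*Combined protocol and SAP*

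**What the plan says.** Reach of the recruitment messages is a secondary objective. Its endpoint is given in Section 1.1 as "Number of visits to recruitment websites by recruitment type" and in Section 3 as "Number of visits to recruitment websites". Section 9.4.3 supplies the analysis: "We will use binomial proportion tests to compare the number of website visits by recruitment message type".

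The design is in Section 4.1: "This comparison will use a factorial design testing the effects of enhancing trust in the researchers", with participant endorsement as the second factor. Section 4.2 likewise describes a test of two components of the message. Section 6.1.1 lists the four resulting postcards: standard alone, standard plus trust, standard plus endorsement, and both.

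Other sections settle much of the rest. Section 6.1.1 gives each message its own site "to allow us to track the reach of the messages via the number of independent website visits". Section 9.3 defines the substudy population as the 4000 addressees less those whose postcards come back. Section 4.1 adds a second reach measure: "Recruitment reach will be assessed through website visits and number of participants responding to each message".

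On routing, Section 5.5 says of postcard recipients: "They will be directed to a study website where a brief description of the study will be presented", and then "Participants recruited through the four recruitment messages will be sent to separate but identical websites". The same section sends people recruited by flyers, a hospital on-hold line or online messages, used as needed, to the study website. It does not say whether that is a page apart from the four.

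**The concern.** A factorial mailing asks two questions: does the trust wording change response, and does the endorsement change response? Each can be answered from all the delivered postcards, half at each level of the factor. A comparison by message type treats the mailing as four separate groups and, if made pair by pair, uses half of the postcards for each contrast. Section 9.4.3 does not say which contrast its tests address, so the analyst would have to choose after seeing the counts, and the reported result might not address either factor directly. At stake is what the substudy can tell future recruitment, which Section 4.2 names as one of its purposes.

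A secondary concern is attribution. Anonymous visits carry no source other than the page on which they land. If visitors from flyers or online messages arrived on a message page, they would be counted for that message and could not be removed later from page counts alone.

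**Working it through.** **Inputs.** From the documents: 4000 addressees (Section 9.3), four messages in a 2x2 layout (Sections 4.1 and 6.1.1), and random assignment with no stated ratio (Section 4.1). The documents give no visit rate, significance level or power for this comparison, so there is no planned figure to reproduce. Assumed: equal allocation, no returned postcards, a two-sided 5% level, and a visit rate of 3% with 2% and 5% as a range.

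**Group sizes.** 4000 / 4 = 1000 per message; 4000 / 2 = 2000 per factor level.

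**Main effect.** With visit rates pS (standard), pT (trust), pE (endorsement) and pTE (both), the Trust main effect is ½[(pT − pS) + (pTE − pE)], and the Endorsement main effect is ½[(pE − pS) + (pTE − pT)]. With 1000 per message and a common rate p, the variance is ¼ × 4p(1 − p)/1000 = 2p(1 − p)/2000.

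**Precision.** The 95% half-width is 1.96 × √(2p(1 − p)/n), with n = 2000 for a main effect and n = 1000 for a message pair. At p = 3%:

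- main effect: 1.96 × √(2 × 0.03 × 0.97/2000) = 0.0106, or 1.06 percentage points
- message pair: 1.96 × √(2 × 0.03 × 0.97/1000) = 0.0150, or 1.50 percentage points

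| Assumed visit rate | Main effect (points) | Message pair (points) |
|---|---|---|
| 2% | 0.87 | 1.23 |
| 3% | 1.06 | 1.50 |
| 5% | 1.35 | 1.91 |

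The ratio is √2, about 1.41, whatever the visit rate.

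**Power.** Power is Φ(|p1 − p2| / √[(p1(1 − p1) + p2(1 − p2))/n] − 1.96):

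| Rates compared | Main effect, n = 2000 | Message pair, n = 1000 |
|---|---|---|
| 2% v 3% | 53% | 30% |
| 3% v 4.5% | 70% | 42% |
| 5% v 7% | 76% | 47% |

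These rows take the same difference in both columns, which is fair when the two factors do not interact. If they do, the main effect is the average of two different effects.

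**Interaction.** The difference of differences, (pTE − pE) − (pT − pS), has half-width 1.96 × √(4p(1 − p)/1000), or 2.11 points at 3%. This is twice that of a main effect, so the four rates are better shown than tested.

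**Outside traffic.** If the same number of outside visitors reaches each page, the constant cancels from every difference between equal-sized groups. If more reach one page, the excess divided by that page's delivered postcards is added to its apparent rate and looks like a message effect. The documents give no volume or distribution for this traffic, so its size cannot be computed from them.

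**The case against.** The strongest reply is that the plan already contains the pieces. Section 4.1 names the two effects, Section 9.3 fixes the population and Section 6.1.1 fixes the unit as independent visits, so a careful analyst would combine them. Sections 4.1 and 9.1 disclaim formal hypotheses, and Section 9.4.1 expects mostly descriptive reporting. For the unit and the denominator this stands: neither needs restating as a defect. For the contrast it stands only in part, because the one sentence that specifies the analysis refers to message type and to neither factor.

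Three stronger readings are tempting, and the documents support none of them. A reader might infer that repeat visits by one man will be tested as if they were separate people; Section 6.1.1 specifies independent visits, and the shorter wording elsewhere does not contradict it. A reader might infer a set of unadjusted pairwise tests; Section 9.4.3 speaks of tests in the plural but does not list pairs, so an inflated error rate cannot be charged to the plan. A reader might infer that outside visitors will contaminate the message pages. Section 5.5 ties the four sites to postcard recruits, the other sources are used only as needed, and a separate page may well be intended. The text is silent; it does not say that the traffic is mixed. Section 6.3 has staff ask which message was received, which helps for people who reach staff but cannot sort anonymous visits.

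**Conclusion.** The point holds as a mismatch between the factorial design in Section 4.1 and the comparison by message type in Section 9.4.3. Main effects give intervals narrower by a factor of √2 than message pairs: 1.06 against 1.50 percentage points at an assumed 3% visit rate. Equal allocation and full delivery are also assumed; returned postcards would widen both intervals. The main effects are the natural summary if the factors act roughly independently, which is why the four rates should be shown beside them.

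The routing question is secondary. It matters only if outside visitors fall unevenly on the message pages. If there are none, or they are evenly spread, the level of the test is not disturbed. Neither part bears on the treatment comparison. Both are modest improvements to a secondary endpoint of a feasibility study.

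**What to change.** 1. In Section 9.4.3, state that the Trust and Endorsement main effects will be estimated on independent visits (Section 6.1.1) per delivered postcard (Section 9.3), as differences in proportions with 95% confidence intervals. List the four message rates descriptively so that an interaction can be seen.
2. Before mailing, add a sentence to Section 5.5 giving flyer, on-hold-line and online recruits their own landing page, excluded from the message comparison, or confirming that this is already the plan.

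The cost is a few lines of text and, if no separate page exists, one more copy of the current page. The mailing, the sample size and the endpoint stay as they are. The downside of the first change is that main effects do not rank the four single messages. A team that wants to pick one postcard would still have to rely on the descriptive rates, with the wider uncertainty shown above.

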9.4.4 SAFETY ANALYSES

N/A

9.4.5 BASELINE DESCRIPTIVE STATISTICS

N/A

9.4.6 PLANNED INTERIM ANALYSES

N/A

9.4.7 SUB-GROUP ANALYSES

N/A

9.4.8 TABULATION OF INDIVIDUAL PARTICIPANT DATA

None

9.4.9 EXPLORATORY ANALYSES

We will explore effect sizes for differences in proportion of participants achieving a 5% weight loss between groups.

10 SUPPORTING DOCUMENTATION AND OPERATIONAL CONSIDERATIONS

10.1 REGULATORY, ETHICAL, AND STUDY OVERSIGHT CONSIDERATIONS

10.1.1 INFORMED CONSENT PROCESS

10.1.1.1 CONSENT/ASSENT AND OTHER INFORMATIONAL DOCUMENTS PROVIDED TO PARTICIPANTS

Consent forms describing in detail the study intervention, study procedures, and risks are given to the participant and written documentation of informed consent is required prior to starting intervention/administering study intervention. A copy of the consent form and consent process documentation form are submitted with this protocol.

10.1.1.2 CONSENT PROCEDURES AND DOCUMENTATION

During the online screening, participants will be asked to read a brief statement about the screening process before they submit their contact information and complete the online screening form. This brief consent will cover only the screening process and associated data. Participants who are eligible to participate in trial will be required to attend an online orientation meeting where the study will be described in detail (described above). Following this, participants will meet with a study staff member individually, in-person to review the consent document. Participants will have time to consider their participation in the study between the orientation session and the consent session. Participants will be given the opportunity to ask questions about the study and will receive answers before the consent is signed. A written signature from the participant will be obtained. Participants will be given a copy of the consent form for their records.

10.1.2 STUDY DISCONTINUATION AND CLOSURE

This study may be temporarily suspended or prematurely terminated if there is sufficient reasonable cause. If the study is prematurely terminated or suspended, the Principal Investigator (PI) will promptly inform study participants, the IRB, and sponsor and will provide the reason(s) for the termination or suspension. Study participants will be contacted, as applicable, and be informed of changes to study visit schedule.

Circumstances that may warrant termination or suspension include, but are not limited to:

- Determination of unexpected, significant, or unacceptable risk to participants
- Demonstration of efficacy that would warrant stopping
- Insufficient compliance of study staff to the protocol (i.e., significant protocol violations)
- Data that are not sufficiently complete and/or evaluable

- Determination that the primary endpoint has been met
- Determination of futility

The study may resume once concerns about safety, protocol compliance, and data quality are addressed, and satisfy the funding agency, sponsor, IRB, Food and Drug Administration (FDA), or other relevant regulatory or oversight bodies (OHRP, DSMB).

10.1.3 CONFIDENTIALITY AND PRIVACY

Participant confidentiality and privacy is strictly held in trust by the participating investigators, their staff, the safety and oversight monitor(s), and the sponsor and funding agency. This confidentiality is extended to the data being collected as part of this study. Data that could be used to identify a specific study participant will be held in strict confidence within the research team. No personally-identifiable information from the study will be released to any unauthorized third party without prior written approval of the sponsor/funding agency.

All research activities will be conducted in as private a setting as possible.

The study monitor, other authorized representatives of the sponsor, representatives of the Institutional Review Board (IRB), or regulatory agencies may inspect all documents and records required to be maintained by the investigator, including but not limited to, medical records (office, clinic, or hospital) and pharmacy records for the participants in this study. The clinical study site will permit access to such records.

Data management support for this project will be provided by the Data Management Center (DMC) within the Rush Department of Preventive Medicine. The DMC has extensive experience in the acquisition, maintenance, and analysis of both large and small clinical trial databases. Risks to privacy and confidentiality will be minimized by following a strict data management protocol. All data will be stored in a de-identified format. Only members of the research team will have access to identifiable private information. All interviewer-administered and self-report questionnaire data will be collected via Snap© survey (Portsmouth, NH) online data capture or REDCap (Research Electronic Data Capture; Nashville, TN) via laptop computers using mobile internet connections/WiFi or paper case report forms. Both Snap and REDCap are fully HIPPA compliant web data collection tools. Both websites and databases are hosted by the Rush Information Services Group.

All Rush issued laptops and tablets are encrypted using Advanced Encryption Standard (AES) algorithm by TrendMicro. No data stored in an encrypted volume can be read without using the correct password. The DMC Server is supported by Rush Information Services. Rush servers are maintained and secured as follows: Rush University has two data centers in Chicago, with one located at [name] and the other at [name] All servers are located in locked data centers with access limited via a biometrics access system to authorized personnel. The data network is segmented and protected from the internet by a Palo Alto firewall. Access to the network from the internet requires multi-factor authentication. All network users are required to have unique logins and passwords. Complex passwords are required, and passwords must be changed every 180 days. Systems are backed up nightly and the data is duplicated and sent to an offsite storage facility.

After the study investigators have had a reasonable period of time to prepare manuscripts, study data sets will be stripped of all PHI to allow sharing of data without compromising participant confidentiality, privacy, and safety. All identification covered under HIPAA will be removed. All remaining variables not covered under HIPAA will be evaluated in terms of risk for deductive disclosure of identity, and appropriate measures will be taken to protect confidentiality.

Measures Taken to Ensure Confidentiality of Data Shared per the NIH Data Sharing Policies It is NIH policy that the results and accomplishments of the activities that it funds should be made available to the public (see <https://grants.nih.gov/policy/sharing.htm>). The PI will ensure all mechanisms used to share data will include proper plans and safeguards for the protection of privacy, confidentiality, and security for data dissemination and reuse (e.g., all data will be thoroughly de-identified and will not be traceable to a specific study participant). Plans for archiving and long-term preservation of the data will be implemented, as appropriate.

Certificate of Confidentiality

To further protect the privacy of study participants, the Secretary, Health and Human Services (HHS), has issued a Certificate of Confidentiality (CoC) to all researchers engaged in biomedical, behavioral, clinical or other human subjects research funded wholly or in part by the federal government. Recipients of NIH funding for human subjects research are required to protect identifiable research information from forced disclosure per the terms of the NIH Policy (see <https://humansubjects.nih.gov/coc/index>). As set forth in 45 CFR Part 75.303(a) and NIHGPS Chapter 8.3, recipients conducting NIH-supported research covered by this Policy are required to establish and maintain effective internal controls (e.g., policies and procedures) that provide reasonable assurance that the award is managed in compliance with Federal statutes, regulations, and the terms and conditions of award. It is the NIH policy that investigators and others who have access to research records will not disclose identifying information except when the participant consents or in certain instances when federal, state, or local law or regulation requires disclosure. NIH expects investigators to inform research participants of the protections and the limits to protections provided by a Certificate issued by this Policy.

